13.3. Secondary Endpoint: Incidence of FACEs

As this is an observational study, patients may switch or stop therapies. If a patient starts dialysis or receives a kidney or heart transplant, the events afterwards will be excluded.

The analysis of the incidence rate (number of patients with at least 1 event per 1000 person-years) will be performed on the Primary and Secondary Effectiveness Populations.

Treatment Switch

The analysis will address events that occur on migalastat or ERT therapy from the Analysis Start Date or switch date up until 30 days after the patient stops therapy or switches therapy. For the patients untreated at enrollment to the study, the analysis will address events from the time of diagnosis until the patient starts a therapy or during periods that they are untreated after a switch.

The second analysis will address events that occur on migalastat or ERT therapy from the Analysis Start Date or switch date. For the patients untreated at enrollment to the study, the analysis will address events from the time of diagnosis until the patient starts a therapy or during periods that they are untreated after a switch.

Analysis Methods

The calculation of the incidence rate (number of events per 1000 person-years) will be performed on the Primary and Secondary Effectiveness Populations.

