## **Rationale and background**

Fabry disease is a rare X-linked lysosomal disorder in lysosomes, resulting in a multisystemic disorder caused by deficiency in the enzyme  $\alpha$ -galactosidase A ( $\alpha$ -Gal A) due to mutations in the GLA gene, encoding the hydrolase  $\alpha$ -Gal A enzyme, which catalyses glycosphingolipids namely globotriaosylceramide (Gb3). Reduced or absent  $\alpha$ -Gal A activity leads to accumulation of Gb3 in the lysosomes of various organs, as well as cellular dysfunction and inflammation causing physical symptoms and eventual organ failure (1,2). Fabry disease as an X-linked disorder with a high penetrance, though not 100% in female heterozygotes, although the disease affects both males and females. With the X-linked nature, Fabry disease is suitable for an efficient, high diagnostic yield cascade screening over at least three generations surrounding an index-patient. The Danish National Fabry Centre has now more than 20 years of experience of cascade screening, which has provided a patient population of 115 male and female patients. The prevalence of Fabry disease in the Danish population is estimated to be 1:58000 (males 1:85000, females 1:44000) (3).

Primarily male patients, with early onset classical phenotypes have none or very low  $\alpha$ -Gal A activity, and they inevitably develop multiorgan failure without treatment (4). Patients with late onset of Fabry disease represent both males and females with higher  $\alpha$ -Gal A activity and variable degrees of organ involvement (5). Fabry disease can cause irreversible damage to multiple organs resulting in Fabry associated clinical events (FACEs) such as renal, cardiac, cerebrovascular events, and death (5).

The primary Fabry specific therapy has historically been enzyme replacement therapy (ERT), and as of 2016 an oral chaperone therapy, Migalastat, has been available, providing an alternative to ERT for patients with amenable mutations by increasing their endogenous  $\alpha$ -Gal A enzyme activity (6–14). However, real-world long-term data from well-characterised cohorts with available detailed clinical consecutive observations with focus on treatment with Migalastat and Fabry associated events has not been fully investigated (12–14).

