### **Method**

Retrospective study of prospectively collected patient data with use of secondary patient data from both paper and electronic patient files. All patients are treatment naïve at time of diagnosis, which is defined as time point for a verified Fabry associated genetic mutation in the GLA gene. A baseline time point is further defined by switch of Fabry specific treatment. Both Migalastat and ERT will be studied retrospectively. Also untreated patients will be studied by assessment of relevant clinical and laboratory variables. The patients have been followed from 01.01.2001 until

31.12.2022. All patients with Fabry disease both receiving specific Fabry medication and untreated patients have been offered assessment yearly or every other year by thorough workup, including targeted examinations of organ function and symptoms known to be associated with Fabry Disease.

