## **Secondary endpoints**

### **The secondary endpoints**

- The prevalence of FACEs from each baseline (diagnosis, and start of treatment) to compare between Migalastat-treated, ERT-treated patients and non-treated patients
- The incidence of FACEs from each baseline (diagnosis, and start of treatment) to compare between Migalastat-treated, ERT-treated patients and non-treated patients

- Time to the first cardiac, cerebrovascular, and renal clinical event separately by each specific category (including death in these categories) from start of treatment or baseline
- Incidence of cardiac, cerebrovascular, and renal clinical events separately by each specific category (including death in these categories)
- Occurrence of cardiac, cerebrovascular, and renal clinical events separately by each specific category (including death in these categories)
- Annualized rate of change in eGFR based on the Chronic Kidney Disease Epidemiology Collaboration equation (eGFRCKD-EPI) over time to compare between Migalastat-treated, ERT, and untreated patients
- The prevalence and incidence of a clinically significant change in mGFR and/or eGFR (according to KDIGO guidelines rapid progression is defined as a sustained decline in eGFR of more than 5 ml/min/1.73 m^2 /yr) from each baseline (diagnosis, and start of treatment) to compare between Migalastat-treated, ERT-treated patients and non-treated pts
- The prevalence and incidence of micro (> 30 mg/g creatinine) or macroalbuminuria (> 300) by urinary albumin/creatinine ratio (ACR) or urinary 24 h protein excretion from each baseline (diagnosis, and start of treatment) to compare between Migalastat-treated, ERT-treated patients and non-treated pts

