3.2. Secondary Effectiveness Analysis

Secondary endpoints listed below will be assessed by evaluating migalastat-treated and untreated patients and/or migalastat-treated and ERT-treated patients:

- The prevalence of FACEs from each baseline (diagnosis, and start of treatment) in migalastat-treated, ERT-treated patients and untreated patients

- The incidence of FACEs from each baseline (diagnosis, and start of treatment in migalastat-treated, ERT-treated patients and untreated patients
- Time to the first cardiac, cerebrovascular, and renal clinical event separately by each specific category (including death in these categories) from baseline (diagnosis and start of each treatment) using Cox proportional hazards model and descriptive statistics.
- Incidence of cardiac, cerebrovascular, and renal clinical events separately by each specific category (including death in these categories)
- Occurrence of cardiac, cerebrovascular, and renal clinical events separately by each specific category (including death in these categories)
- Annualized rate of change in eGFR based on the Chronic Kidney Disease Epidemiology Collaboration equation (eGFR CKD-EPI) over time in migalastat-treated, ERT, and untreated patients . Analysis will also be performed by eGFR category at baseline if the counts are sufficient.
- The prevalence and incidence of a clinically significant change in mGFR and/or eGFR (according to KDIGO guidelines rapid progression is defined as a sustained decline in eGFR of more than 5 ml/min/1.73 m²/yr) from each baseline (diagnosis, and start of treatment) in migalastat-treated, ERT-treated patients and untreated patients.
- The prevalence and incidence of micro (> 30 mg/g creatinine) or macroalbuminuria (> 300) by urinary albumin/creatinine ratio (ACR) or urinary 24 h protein excretion from each baseline (diagnosis, and start of treatment) in migalastat-treated, ERT-treated patients and untreated patients.

The analysis for the primary effectiveness endpoint will be performed at the 2-sided significance level of 0.05 to compare migalastat-treated and untreated patients. All other comparisons will also be done at the 2-sided significance level of 0.05 with no adjustment for multiple comparisons.

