7.3. Statistical Reporting

Statistical analyses will be reported using summary tables, figures, and data listings. Continuous variables will be summarized with counts, means, standard deviations, medians, minimums, and maximums. Categorical variables will be summarized by counts and by percentage of patients. For event data, i.e., SAEs and the exposure-adjusted incidence rates will be summarized as

counts of patients with a new event per 1000 person-years exposure, with a 95% confidence interval (CI) using Ulm's method (Ulm 1990).

Recurrent events will be presented for SAEs and each specific FACE and will be shown as a total count of each event per 1000 person-years.

A Cox proportional hazards model will be used for the summary of time to event data.

Tables, listings, and figures will be presented in rich text file (RTF) format. Upon completion, all SAS programs will be validated by an independent programmer. In addition, all programmed outputs will undergo a senior level statistical review. The validation process will be used to confirm that statistically valid methods have been implemented and that all data manipulations and calculations are accurate. Checks will be made to ensure accuracy and consistency with this plan, consistency within tables, and consistency between tables and corresponding data listings. Upon completion of validation and quality review procedures, all documentation will be collected and filed by the project statistician or designee.

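### FACE incidence is compared between treatments as crude person-year rates, with no adjustment for attained age, and the planned age subgroup does not supply it

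*SAP*

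**What the plan says.** **The measure.** SAP 13.3 gives the FACE incidence calculation as follows: "The calculation of the incidence rate (number of events per 1000 person-years) will be performed on the Primary and Secondary Effectiveness Populations". Earlier in the same section the numerator is different: "number of patients with at least 1 event per 1000 person-years". Neither form carries a covariate. SAP 7.3 adds an interval for a single exposure-adjusted rate, "with a 95% confidence interval (CI) using Ulm's method", but no contrast between rates.

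**How person-time is assigned.** Migalastat or ERT time runs from the Analysis Start Date or a switch date. Untreated time runs from diagnosis to the start of therapy, "or during periods that they are untreated after a switch". One patient can therefore add person-years to more than one group.

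**What the rates are for.** The Protocol's list of secondary endpoints gives FACE incidence from each baseline "to compare between Migalastat-treated, ERT-treated patients and non-treated patients". SAP 3.2 adds a general rule: "All other comparisons will also be done at the 2-sided significance level of 0.05 with no adjustment for multiple comparisons". SAP 13.8 (GFR decline) and 13.9 (albuminuria) state a comparison of the three groups and adopt the FACE incidence and prevalence methodology.

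**The order of treatment.** The Protocol's Method section says: "All patients are treatment naïve at time of diagnosis". Its background section says that "as of 2016 an oral chaperone therapy, Migalastat, has been available".

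**Age and sex elsewhere.** The Cox model in SAP 13.1.1 adjusts for sex and for age at the Analysis Start Date. SAP 12 plans subgroups by sex and by age (cut at 40). The Protocol's Descriptive statistics section stratifies by sex and age, and its Secondary endpoints analysis section plans incidence by phenotype and sex, subject to data.

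**The concern.** A crude rate by current treatment compares whatever patients, at whatever ages, happen to supply the person-time. When a patient changes to migalastat, the earlier years stay in the untreated or ERT denominator and the later, older years enter the migalastat denominator. If FACE rates rise with age, part of any rate difference is ageing rather than drug. Within such patients the distortion works against migalastat.

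The formal primary analysis uses the initial treatment cohort (SAP 3.1), so the incidence endpoint is one of the main places where switchers' migalastat years are counted. The same method passes to the GFR and albuminuria endpoints. Because one patient can appear in several groups, the rates are also not independent, and single-rate intervals do not allow for that.

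At stake is a between-treatment statement that could suggest harm or hide benefit, and that may differ from the adjusted Cox result for reasons unrelated to the drug.

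**Working it through.** The plan gives no FACE rate, event count, power or treatment-specific age or sex mix, so it has no figure to reproduce. What follows combines the documents' dates with stated assumptions.

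**Step 1: age gap within one patient.** If *a* years before migalastat are followed directly by *b* years on it, mean age differs by (a + b)/2. Follow-up from 2001 to the end of 2022 (Protocol) is 22 years; to the end of 2023 (SAP) it is 23 years.

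| Diagnosed at start of | Gap, end 2022 | Gap, end 2023 |
|---|---|---|
| 2001 | 22/2 = 11.0 years | 23/2 = 11.5 years |
| 2006 | 17/2 = 8.5 years | 18/2 = 9.0 years |
| 2011 | 12/2 = 6.0 years | 13/2 = 6.5 years |

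**Step 2: spurious rate ratio for that patient, no drug effect.** Let the rate multiply by *g* per decade and k = ln(g)/10. The ratio is [(e^(k(a+b)) − e^(ka))/(kb)] ÷ [(e^(ka) − 1)/(ka)]. Migalastat start in mid-2016 is assumed. For 2001 diagnosis, a = 15.5 and b = 6.5 (or 7.5 with the SAP end date):

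- g = 1.3: 1.33 to 1.35
- g = 1.5: 1.54 to 1.57
- g = 2.0: 2.06 to 2.14

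For 2011 diagnosis with the Protocol end date (a = 5.5, b = 6.5), the values are 1.17, 1.28 and 1.52.

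**Step 3: whole cohort, no drug effect.** This was a simulation of 115 patients, one third male (both from the documents), with 500 runs per value of *g*. Assumptions: male:female rate ratio 2; female rate 25 per 1000 person-years at age 40; diagnosis age mean 40, SD 15; 50% of males and 35% of females reach migalastat; follow-up to the end of 2022; no switching back; untreated and ERT time pooled as comparator; all events counted.

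| g | Crude rate ratio | Crude, diagnosed at ≤40 | Crude runs significant | Adjusted median rate ratio | Adjusted runs significant |
|---|---|---|---|---|---|
| 1.3 | 1.22 | 1.22 | 11% | 0.97 | 5.0% |
| 1.5 | 1.31 | 1.31 | 24% | 0.99 | 5.6% |
| 2.0 | 1.52 | 1.50 | 55% | 1.00 | 6.4% |

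The adjusted column is Poisson regression with a log person-years offset, attained age and sex. Restricting to patients diagnosed at 40 or younger leaves the crude ratio almost unchanged, because time since diagnosis still separates the groups.

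**Step 4: how much of Step 3 is sex.** The assumed uptake makes the male share of migalastat users (1/3 × 0.50)/(1/3 × 0.50 + 2/3 × 0.35) = 0.417. Against a comparator share of about one third, sex alone gives (1 + 0.417)/(1 + 0.333) ≈ 1.06. Dividing it out leaves roughly 1.15, 1.23 and 1.43 for age.

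**Step 5: sex mix in general.** With male:female rate ratio *m* and male shares p, the ratio is (1 + (m − 1)p_mig)/(1 + (m − 1)p_comp). For m = 1.5 to 3:

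- equal shares: 1.00
- 40% v 20% male: 1.09 to 1.29
- 30% v 40% male: 0.96 to 0.89

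**Step 6: the reverse order.** The example patient in SAP 13.1.2 takes migalastat to Month 9, is untreated to Month 24, then starts ERT. Mean time is 9/2 = 4.5 months on migalastat and (9 + 24)/2 = 16.5 months untreated. Here the migalastat time is 12 months *younger*, so the age bias changes sign.

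**The case against.** The strongest reply is that formal inference lies elsewhere and is adjusted there. SAP 13.1.1 adjusts for sex and age, 13.1.2 uses time-dependent treatment, and 13.4 carries the 13.1 methods to each event category. SAP 13.3 itself names no test or rate ratio, and the incidence bullet in SAP 3.2 drops the Protocol's comparison wording. Sex and age subgroups are planned as well.

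Part of this stands. Sex-specific rates would separate sex, so the sex concern applies only to the pooled rate. That a test will be run on these rates is inferred from the general significance rule in 3.2. But the Protocol states the comparison, SAP 17.1 declares no change from the Protocol, and 13.8 and 13.9 state comparisons by the same method. The age subgroup fixes age at diagnosis (against untreated) or at treatment start (against ERT), and the Protocol's conditional incidence subgroups have no age split. The interval-based Cox model names no covariates and does not adjust the rates.

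A reader might infer three stronger claims that the documents do not support:

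- *Migalastat time is always older time.* This holds only against the same patient's own earlier years. Patients who start within 3 months of enrolment count as migalastat from the outset (SAP 5.2.1), never-treated patients may be of any age, and switches back are foreseen. The net age gap between groups is not fixed.
- *Sex imbalance inflates the migalastat rate.* Classical disease being mainly in males does not show who receives migalastat, and the primary population is limited to amenable variants. No sex mix by treatment is given, so the direction is unknown.
- *The crude rates will contradict the Cox result.* They may differ; nothing shows that they must.

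**Conclusion.** The concern holds in limited form. The incidence comparison in SAP 13.3 is unadjusted, it is confounded by attained age for patients who move to migalastat, and the planned subgroups do not correct that. With no drug effect, the simulated crude rate ratio was about 1.2 to 1.5, or about 1.15 to 1.4 once the assumed sex imbalance is divided out.

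These sizes depend on the assumed 1.3 to 2.0 rise per decade, the uptake pattern and one-way movement to migalastat, none of which the documents give. With balanced groups the bias is nil; with early migalastat starts or switches back it can reverse. The simulation drew events independently within patients, so it says nothing about how far clustering alone widens the intervals. The change is worth making before analysis, but the documents do not establish that the reported comparison will be materially wrong.

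**What to change.** In SAP 13.3:

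1. Name the between-treatment comparison as a rate ratio from a Poisson model with a log person-years offset. Split person-time at treatment changes and by attained age. Include time-updated treatment, attained age and sex, with previous FACE if events allow, and cluster the variance on patient. If events are few, use age- and sex-standardised rates instead.
2. State which numerator it uses: patients with at least one event, or all events. The section now gives both. If it is patients with a first event, say when person-time stops.
3. Label the crude rates descriptive.
4. Correct the cross-references. SAP 13.5 (incidence by category) points to 13.2, which is prevalence, and 13.6 (prevalence by category) points to 13.3, which is incidence. Without this, the change would not reach category incidence.
5. Confirm that 13.8 and 13.9 follow the revised method for their incidence parts.

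The cost is SAP wording and programming; date of birth, sex, treatment dates and event dates are already collected. The downside is limited precision: with about 115 patients and an unknown event count, adjustment may have to stop at age and sex.

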13.4. Secondary Endpoint: Time to first FACE by Category

Time to the first cardiac, cerebrovascular, and renal clinical event separately by each specific category (including death in these categories) from start of treatment or time of diagnosis will be analysed in the same way as the primary endpoint - composite FACEs (section 13.1).

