4. SAMPLE SIZE JUSTIFICATION

Approximately 115 patients with established Fabry Disease, estimated 2/3 female and 1/3 male.

Sample size was not determined statistically. All patients from Danish National Fabry Centre are included.

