13. ANALYSIS OF EFFECTIVENESS

13.1. Primary Endpoint

The comparison of interest is between migalastat-treated and untreated patients in the Primary and Secondary Effectiveness Populations. The analysis for the primary effectiveness endpoint will be performed at the 2-sided significance level of 0.05. This analysis will be performed when enough data are available.

Clinical effectiveness will be based on FACEs of cardiac, cerebrovascular, and renal events, and deaths due to FACEs. A composite event is defined as the occurrence of either cardiac, cerebrovascular, or renal clinical event, and death due to FACEs.

Subject matter experts will adjudicate all reports of FACEs. For all summary analyses, the adjudicated decisions will be used if they differ from the initial report. Both original and adjudicated decisions will be reported in listings. Only adjudicated decisions will be used for analyses.

Analyses will be performed in the Primary and Secondary Effectiveness Population.

The analyses described further in Section **Error! Reference source not found.** through Section **Error! Reference source not found.** will be performed for the endpoint of all FACEs combined and separately for all specific FACEs categories listed above (including deaths in these categories) as supportive analyses. A separate analysis of all deaths due to FACEs will also be conducted.

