13.1.1. Cox Proportional Analysis for Fabry-associated Clinical Events

The time to the first event is defined as time from the Analysis Start Date to the first composite FACE (primary interest), and to the first cardiac, cerebrovascular, renal clinical event, or death due to FACEs. For the primary analysis, patients who complete the study without an event, are lost to follow-up, discontinued the study, started dialysis, had a kidney or heart transplant, or after 30 days they changed/switched therapy (migalastat group) or after they start therapy (untreated group) will be censored. Describing effectiveness in migalastat treated population is of the main interest.

Treatment Switch

The primary analysis will address events that occur on therapy from the Analysis Start Date up until 30 days after the patient stops therapy or switches therapy. The events that happen afterwards will be excluded. For the patients untreated at time of diagnosis, the primary analysis will address events from the time of diagnosis until the patient starts a therapy. The events that happen afterwards will be excluded. An additional analysis will be performed:

1. An analysis that will address events that occur on therapy from the time of Analysis Start Date up until the patient stops therapy or patient switches therapy. For the untreated patients, the analysis will address assessments from the time of diagnosis until the patient starts a therapy. The events that happen afterwards will be excluded.

Primary Analysis Method

The ratio of the hazards of treatment groups will be checked to ensure that the hazard ratios are constant over time. Secondly, the assumption that each variable in the model makes a linear contribution will be checked.

The covariates will include:

- sex
- age at the Analysis Start Date as a continuous variable
- eGFR_{CKD-EPI} at the Analysis Start Date as a continuous variable
- LVMi at the Analysis Start Date
- previous history of cardiac, cerebrovascular, and renal clinical events (composite event) as related to Analysis Start Date
- Length of treatment for Fabry disease

If the measurements are not available, measurements prior to and closest to the Analysis Start Date will be used. In case that more than 50% of values are missing for a given covariate, it will be dropped from the analysis.

The estimate of hazard ratio for migalastat-treated/untreated along with the associated 95% CI will be calculated.

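### The seven-parameter Cox model is planned for every FACE category and for FACE deaths with no fitting method or rule tied to event counts, so the sparser endpoints risk infinite hazard ratios

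*SAP*

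**What the plan says.** SAP 13.4 states that time to the first event in each category "will be analysed in the same way as the primary endpoint - composite FACEs (section 13.1"). SAP 3.2 names the method for these endpoints as "using Cox proportional hazards model and descriptive statistics". SAP 13.1 asks for the composite and, "separately for all specific FACEs categories listed above (including deaths in these categories) as supportive analyses", and adds: "A separate analysis of all deaths due to FACEs will also be conducted". SAP 13.1.1 lists FACE death among its time-to-event outcomes.

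The model in SAP 13.1.1 has treatment plus sex, age, eGFR, LVMi, previous FACE and length of Fabry treatment, which makes seven parameters. The protocol's primary analysis section lists three covariates. The required output is explicit: "The estimate of hazard ratio for migalastat-treated/untreated along with the associated 95% CI will be calculated". Analyses are run in both effectiveness populations, and the primary one admits only patients with an amenable variant.

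On size, SAP 4 gives "Approximately 115 patients with established Fabry Disease, estimated 2/3 female and 1/3 male" and says "Sample size was not determined statistically". On testing, SAP 3.2 says "All other comparisons will also be done at the 2-sided significance level of 0.05 with no adjustment for multiple comparisons".

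Three texts bear on sparse data:
- SAP 13.1 makes the primary analysis conditional on having sufficient data, with no number and no fallback.
- SAP 13.1.1 drops a covariate when more than half of its values are missing.
- SAP 12 allows descriptive statistics only, but for small subgroups.

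None of them refers to the number of events.

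**The concern.** If no patient on migalastat has an event in a category, the partial likelihood keeps rising as the treatment coefficient falls. The estimated hazard ratio is then zero with no finite standard error. With a handful of events, combinations of covariates can produce the same divergence even when migalastat patients do have events.

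The design makes low counts plausible. About 115 patients are split over three groups, and each comparison uses two of them. SAP 3.1 bases the formal analysis on the initial treatment cohort. The protocol dates migalastat availability to 2016, so time on that drug is short against follow-up of more than 20 years.

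What is at stake is an uninterpretable estimate for the contrast of main interest. A near-zero migalastat hazard ratio could be read as benefit when it only reflects separation. If the problem appears at analysis, the remedy would be chosen with the results in view.

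**Working it through.** **No plan figure to reproduce.** Neither document gives expected events, group sizes or a power calculation. Everything below on events and group shares is an assumption, shown as a range.

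**Step 1. Events per parameter** (total events divided by 7): 5/7 = 0.7; 10/7 = 1.4; 20/7 = 2.9; 40/7 = 5.7.

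**Step 2. Chance of no migalastat event.** Take 20 patients followed for 5 years, or 100 person-years. The Poisson probability of zero is exp(-100 x rate). At 5, 10 and 20 events per 1000 person-years this is exp(-0.5) = 61%, exp(-1) = 37% and exp(-2) = 14%. Alternatively, if 10% of all events fall on migalastat, the chance of none is 0.9^5 = 59%, 0.9^10 = 35% and 0.9^20 = 12%.

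**Step 3. Simulation of the seven-parameter model** (600 to 1000 data sets per setting). Assumptions: 115 patients (the upper bound) or 60; 30%, 40% or 50% on migalastat; true HR 0.5 or 1; moderate covariate effects; follow-up 0.5 to 6.5 years on migalastat and 0.5 to 15 years untreated. A treatment estimate counts as infinite if its standard error exceeds 10 or |log HR| exceeds 8. Share infinite with standard partial likelihood:

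| Assumed setting | 5 events | 10 | 15 | 20 | 30 | 40 |
|---|---|---|---|---|---|---|
| 115 patients, 30% migalastat, HR 0.5 | 63% | 37% | 22% | 11% | 2% | 0.2% |
| Same, length of treatment zero in untreated | not run | 41% | not run | 14% | not run | 0.7% |
| 60 patients, 40% migalastat | 56% | 22.5% | 6% | 1% | 0% | not run |
| 115 patients, 50% migalastat, HR 1 | 29% | 6% | not run | 0.3% | not run | 0% |

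A separate null simulation (60 patients, 20 on migalastat, six parameters) gave 38%, 15%, 2% and 0% at 5, 10, 20 and 35 events.

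**Step 4. Firth fit.** This maximises l(b) + 0.5 log|I(b)|, where l is the log partial likelihood and I the information matrix. The profile interval holds all b for which twice the drop in penalised log likelihood is at most 3.84.
- Treatment HR outside 1/50 to 50 (115 patients, 30% migalastat, HR 0.5): 1.1% at 5 events, 0.4% at 10, none from 15. With 60 patients: 3.4% and 1.3% at 5 and 10 events.
- Profile coverage at 5, 10, 20, 30, 40 and 60 events: 93.9%, 95.8%, 96.3%, 95.3%, 95.0% and 94.7%. Firth Wald intervals over-cover at very low counts (up to 99.7% at 5 events).
- Data sets where the standard fit diverged at 10 events (30% migalastat): standard median HR about 1e-11 with standard error about 250,000; Firth median HR 0.29, median limits 0.002 to 2.9, always finite.
- Cost when events are ample (115 patients), root mean square error of log HR, Firth against standard: 0.51 against 0.56 at 40 events, 0.38 against 0.40 at 60.

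**Step 5. What Firth does not do.** Over all data sets at 30% migalastat, the median profile limits were about 0.009 to 8.7 at 5 events and 0.06 to 4.0 at 10. Schoenfeld power for HR 0.5 with a 30% share is Phi(|ln 0.5| x sqrt(0.21 x D) - 1.96), which is 17% at D = 10 and 30% at D = 20. For 80% power, D = (1.96 + 0.84)^2 / (0.21 x 0.693^2), or 78 events.

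**The case against.** The strongest reply is that the plan already protects the reader.
- SAP 13.1.1 adds a Kaplan-Meier and log-rank sensitivity analysis, which survives an arm with no events. Under a null scenario with assumed inputs it rejected in 2%, 4%, 7% and 6% of runs at 5, 8, 12 and 20 events.
- SAP 7.3 and 13.2 to 13.6 plan counts, prevalence and rates per 1000 person-years by category, so a zero on migalastat would be visible beside any hazard ratio.
- SAP 13.1 calls the category analyses supportive.
- Its sufficient-data proviso plausibly carries into 13.4 through the cross-reference, so an HR is not demanded whatever the data.
- SAP 13.1.2 adds a Cox model using all treatment periods.

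All of this stands. It limits the harm, but it gives no threshold, and none of the log-rank, count or rate analyses supplies an adjusted hazard ratio. The interval-based model is also a Cox fit, with no sparse-event rule of its own.

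A reader might infer more than the documents support:
- That every category will fail. Event counts are unknown, and divergence is rare from 30 to 40 events.
- That the SAP prescribes Wald intervals. It leaves the interval method open; Wald is only a likely software default.
- That Firth would rescue power. With a true HR of 0.25, rejection at 5 events was 0% for Wald and 5% for Firth; at 12 events it was 2% and 18%. Firth helps at moderate counts, not at the lowest.
- That covariates should simply be cut when events are few. Dropping eGFR, LVMi and previous FACE from a non-randomised comparison trades separation for confounding.

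**Conclusion.** The point holds as a conditional risk. The plan sends every FACE category and FACE deaths to a seven-parameter Cox model in at most about 115 patients, and states neither a fitting method nor an event-based rule. If a category has about 5 events, a standard fit gives an infinite migalastat hazard ratio in roughly 29% to 63% of data sets. At 10 events the range is 6% to 41%, where the upper figure has length of treatment set to zero in untreated patients. From 30 to 40 events it is about 2% or less.

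These figures rest on assumed event counts, group shares, covariate effects and follow-up. The 115 is an upper bound, because each fit uses two groups and the primary population only amenable patients. Length of treatment overlaps with the treatment term. That is a separate collinearity problem which penalisation only partly relieves: in that setting Firth still gave an HR outside 1/50 to 50 in 4.5% of data sets at 10 events.

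**What to change.** In SAP 13.1.1 and 13.4, state that the Cox models are fitted with Firth's penalised partial likelihood, with profile penalised-likelihood 95% intervals and penalised likelihood-ratio tests. SAS PHREG offers this as options. Raise the iteration limit: at 5 events only 74% to 84% of Firth fits converged within 40 iterations, against 98% with 200 in the one setting tested.

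Replace the open proviso in SAP 13.1 with a minimum event count, fixed before the data are seen and applied to each category and to FACE deaths. Below it, report counts, person-years and rate intervals without a hazard ratio. The interval widths in the working can guide the choice. If a reduced covariate set is wanted for low counts, the sponsor's statistician should pre-specify it and weigh the confounding it admits.

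The cost is a few sentences and a procedure option. The statistical downside is slight shrinkage of the hazard ratio, negligible from about 20 events. The change prevents degenerate estimates; it does not add information, and intervals at 5 to 10 events will remain very wide.
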